## 9 ADVERSE EVENT REPORTING

# 9.1 Definition

An 'adverse event' following a procedure is also referred to as an adverse experience. It refers to any untoward medical occurrence in a clinical investigation participant which may or may not have a causal relationship with that procedure. An adverse event can therefore be any unfavourable and unintended sign, symptom, or disease associated with the procedure.

*BCL6 as an endometriosis biomarker* Protocol Version 5, 26/08/2021 Page 21 of 47

#### 9.2 Eliciting Adverse Event Information

Included in the 'Patient Information and Consent' form is an outline of potential adverse events post-operatively (such as infection) (please see Appendix 13.2). Patients will be encouraged to contact the research team should they develop any concerning symptoms post-operatively (e.g. temperature  $\geq$  38.0, malodorous vaginal discharge, worsening abdominal pain etc).

An adverse event checklist will be completed at both the first and second follow-up consultation post-operatively, along similar lines.

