#### 4.3 Number of Participants

184. We will need to recruit 68 patients who are found to have endometriosis at laparoscopy, and 116 who are not.

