#### **5 STUDY TREATMENTS**

Some participants in this study would already be planning to undertake endometrial biopsy, in addition to planned laparoscopy (for example, to investigate heavy menstrual bleeding). Others may originally only be planning to undertake laparoscopy, and will (if they participate) undergo an endometrial biopsy (as part of this study), over and above the planned laparoscopy.

While the patient is anaesthetised, endometrial biopsy will be performed using a 'dilatation and curettage' technique. This involves:

- Gently dilating the cervical canal up to 5mm diameter, using 'cervical dilators'
- Using a 'curette' to take a sample of the lining of the uterus ('endometrium')

This procedure is outlined in the attached 'Patient information and consent' form, as are the potential complications, including:

- Uterine perforation (approximately 1 in 300 women)
- Formation of intra-uterine adhesions (scar tissue) (approximately 1 in 60 women)
- Cervical injury (approximately 1 in 25 women)
- Infection (approximately 1 in 20 women)
- Blood loss > 100mLs (approximately 1 in 10 women)

(Please see Appendix 13.2 for this document.)

The potential implications of the above possible complications and their management include:

(1) Uterine perforation: collection of blood tests for full blood count; injury to bladder or bowel

(1 in 15 patients who have a uterine perforation); intra-abdominal haemorrhage (1 in 6
patients who have a uterine perforation); need for laparotomy (very rare)

*BCL6 as an endometriosis biomarker* Protocol Version 5, 26/08/2021 Page 16 of 47

- (2) Intra-uterine adhesions: lighter menstruation (4 in 5 women with intra-uterine adhesions); sub-fertility (1 in 8 women with intra-uterine adhesions); cyclic pelvic pain (1 in 30 women with intra-uterine adhesions); recurrent pregnancy loss (1 in 8 women with intra-uterine adhesions). Management of the above issues involves hysteroscopy (a procedure performed under general anaesthetic to visualise the lining of the uterus with a small video camera), and resection of the intra-uterine adhesions (separating the intra-uterine scarring, using 'diathermy' electrosurgical devices).
- (3) Cervical injury: repair of any cervical tear is performed immediately, using several absorbable stitches.

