- (4) Infection: mild infections (the majority) are treated with tablet antibiotics; severe infections (very rare) require admission to hospital and intravenous antibiotics.
- (5) Blood loss > 100mLs: observation; collection of blood tests for full blood count; administration of medications such as syntocinon and/or tranexamic acid; in the cases of very rare major haemorrhage (> 1000mLs), laparotomy (open surgery) may be needed

The above potential complications of dilatation and curettage can be compared with the potential risks of laparoscopic surgery, which include the following:

- Conversion to an open operation ('laparotomy') (approximately 1 in 70 women)
- Injury to urinary tract (bladder or ureters) (approximately 1 in 100 women)
- Injury to major (big) blood vessel (approximately 1 in 200 women)
- Injury to minor (small) blood vessel (approximately 1 in 350 women)
- Later development of hernia through one of the scars (approximately 1 in 500 women)
- Injury to gastrointestinal tract (stomach or bowels) (approximately 1 in 1000 women)

After the endometrial biopsy tissue has been sent to Douglass Hanly Moir (DHM) pathology laboratories, they will be analysed to assess the BCL6 level. DHM then routinely stores all pathology slides and paraffin block for ten years. After this point, samples are incinerated.

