#### 6.7 Trial Closure

All participants will receive follow-up through our private gynaecology clinic. This involves: a telephone call from our clinic nurse at approximately 1 week post-operatively (henceforth known as 'follow-up 1'); and two phone calls at approximately 4 weeks post-operatively ('follow-up 2'). One phone call will be from the Principal Investigator, to explain to the patient the stage of endometriosis (if present), and their BCL6 HSCORE. The other phone call will be from the clinic nurse, to ask if they have experienced any complications, such as uterine perforation, fever, or post-operative haemorrhage. If any patient reports any complications, the nurse will escalate immediately to the Principal Investigator.

Should any patient have any concerns post-operatively, they are welcome to call our clinic to discuss these concerns over the phone, and/or to come in for consultation.

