# Severity of endometriosis:

Endometriosis		< 1cm	1 to 3cm	> 3cm
Peritoneum	Superficial	1	2	4
	Deep	2	4	6
Right ovary	Superficial	1	2	4
	Deep	4	16	20
Left ovary	Superficial	1	2	4
	Deep	4	16	20
PoD obliteration	Partial	4		
	Complete	40		
Adhesions		< 1/3 enclosure	1/3 to 2/3	> 2/3 enclosure
Adhesions Adhesions right ovary	Filmy	< 1/3 enclosure	1/3 to 2/3	> 2/3 enclosure
	Filmy Dense			
		1	2	4
Adhesions right ovary	Dense	1 4	2 8	4 16
Adhesions right ovary	Dense Filmy	1 4	2 8 2	16
Adhesions right ovary  Adhesions left ovary	Dense Filmy Dense	1 4 1	2 8 2 8	4 16 4 16
Adhesions right ovary  Adhesions left ovary	Dense Filmy Dense Filmy	1 4 1 4	2 8 2 8	4 16 4 16 4

Points scored on rASRM classif	ication: 0 / 1 to !	5 / 6 to	15 / 16 to 40 / > 40		
Severity of endometriosis:	e I / stage II / stage IV				
BCL6 result:					
Date of first follow-up:	//				
Adverse events reported:	Uterine perforation		Cervical injury		
	Intra-operative blood loss > 100mLs				
	Fever >38.0		Post-op haemorrhage		
Date of second follow-up:	//				
BCL 6 result given to patient					
Stage of endometriosis reported to patient					
Adverse events reported:	Uterine perforation		Cervical injury		
	Intra-operative blood loss > 100mLs				
	Fever >38.0	П	Post-on haemorrhage

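### The visible CRF checklist records infection, quoted at 1 in 20, only through a fever box, and its first follow-up list has no field for other or serious events

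*Protocol*

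**What the plan says.** Section 5 lists five complications of the biopsy with approximate rates: blood loss above 100 mL (1 in 10), infection, cervical injury (1 in 25), intra-uterine adhesions and perforation (1 in 300). For infection it says "Infection (approximately 1 in 20 women" and for adhesions "Formation of intra-uterine adhesions (scar tissue) (approximately 1 in 60 women". It adds that "mild infections (the majority) are treated with tablet antibiotics".

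Section 9.2 asks patients to contact the team about concerning symptoms. Its examples are a temperature of 38.0 or more, then "malodorous vaginal discharge, worsening abdominal pain etc". The next sentence but one sets up the follow-up checklist: "An adverse event checklist will be completed at both the first and second follow-up consultation post-operatively, along similar lines".

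The schedule in section 7 marks an adverse event and serious event assessment at both follow-ups. Section 6.7 places these at about 1 week and about 4 weeks. At the second, the clinic nurse is "to ask if they have experienced any complications, such as uterine perforation, fever, or post-operative haemorrhage".

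The CRF gives the same list under each follow-up date: uterine perforation, cervical injury, "Intra-operative blood loss > 100mLs", fever above 38.0 and post-operative haemorrhage. Section 9.3 says that all possible adverse events go into the study log.

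**The concern.** The form does not match the sections it is meant to serve. Section 9.2 ties the checklist to three symptoms, and the form carries one of them. Section 5 ranks infection second among the five complications, and the form records it only if the woman had a fever. Section 7 requires a serious event assessment at both calls, and the first list gives it no field.

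Three of the five items (perforation, cervical injury, intra-operative blood loss) arise chiefly in theatre, where the surgeon would normally know of them. Infection is the listed complication for which a telephone call in the first weeks is most informative, and its item is the weakest.

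What is at stake is safety capture, not the diagnostic accuracy result. Some women have the biopsy only because of the study. If mild infections are recorded only when someone happens to mention them, any complication rate quoted later would tend to be too low, and a cluster during recruitment could be noticed late.

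**Working it through.** **Passages side by side**

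| Event or symptom | Section 5 | Section 9.2 | CRF, each follow-up |
|---|---|---|---|
| Perforation | 1 in 300 | – | item |
| Cervical injury | 1 in 25 | – | item |
| Blood loss > 100 mL | 1 in 10 | – | item |
| Infection | 1 in 20 | general example | no item of its own |
| Fever | – | ≥ 38.0 | item, > 38.0 |
| Malodorous discharge | – | named | none |
| Worsening abdominal pain | – | named | none |
| Adhesions | 1 in 60 | – | none |
| Post-operative haemorrhage | – | – | item |
| Other (free text) | – | – | none in first list |
| Serious event | – | – (scheduled in section 7) | none in first list |

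**Inputs.** N = 184 (section 4.3: "184. We will need to recruit 68 patients who are found to have endometriosis at laparoscopy, and 116 who are not"; 68 + 116 = 184). Infection rate 1/20 and adhesion rate 1/60 (section 5). The protocol states no expected number of complications, so there is no figure of that kind to reproduce.

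**Expected infections.** 184 × 1/20 = 9.2. The chance of at least one is 1 − 0.95^184 = 0.9999, so an infection item would almost certainly be used.

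**Expected infections with no matching CRF item.** Let f be the share of infections with a fever that ticks the box. The count is 9.2 × (1 − f). The protocol does not give f, so the values below are assumptions:

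| f | 9.2 × (1 − f) |
|---|---|
| 0% | 9.2 |
| 50% | 4.6 |
| 75% | 2.3 |
| 100% | 0 |

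Section 5 says that most infections are mild. That makes f = 100% unlikely, but it does not fix f, because mild is not the same as afebrile.

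**Share due to the study.** Section 4.2 says many participants were already planning a biopsy. If s is the share biopsied only for the study, the count becomes 9.2 × s × (1 − f). With s and f both assumed to be 50%, it is 9.2 × 0.5 × 0.5 = 2.3.

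**Adhesions.** 184 × 1/60 = 3.1 expected. Section 5 describes their effects as lighter periods, sub-fertility, cyclic pain and pregnancy loss. The last contact is a telephone call at about 4 weeks, when most of these may not yet be apparent. A tick box at that call would find few of them, so they are not added to the count.

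**The case against.** The strongest reply is that the checklist is not the only safety net. At follow-up 2 the nurse asks about any complications, and the named ones are only examples. A woman given antibiotics for an afebrile infection has every chance to say so. Any reported complication is escalated at once to the principal investigator (section 6.7), and section 9.3 sends all possible events to the study log. Fever, the first symptom in 9.2, does have an item at both calls.

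The 9.2 symptoms are also only examples, and the checklist need only run on similar lines, so the missing items are a loose fit rather than a flat contradiction. Complication rates are not among the objectives or outcome measures. The visible CRF text ends at the second list, so a later free-text or serious-event field cannot be excluded. The fever wording differs only at exactly 38.0.

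Much of this stands. A reader might add the two complications without their own item, 9.2 + 3.1 = 12.3, and infer that about 12 events would go systematically unrecorded. The documents do not support that. The fever item catches an unknown share of the infections, the open question and the log offer further routes, and the adhesions are limited by the length of follow-up rather than by the form.

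The reply does not remove the gap. The open question is described only for week 4, its examples name neither infection nor the two missing symptoms, and the visible form has no field for the answer. The log records what reaches it, and section 9.3 does not say how an event that nobody asked about would get there.

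**Conclusion.** The point holds as a modest one about data capture. The visible CRF records infection only through fever, omits two of the three symptoms named in 9.2, and in its complete first list has no field for other or serious events despite the schedule in section 7. Afebrile infections therefore rest on the open question at follow-up 2, spontaneous report and the study log.

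The number of infections without a CRF item lies between 0 and about 9 among 184 women. This assumes that the section 5 rate applies to this population and that all 184 are biopsied. It counts infections with no form item, not infections lost, since the other routes will recover some. The number due to study-only biopsies is smaller and cannot be determined from the protocol. The primary analysis is unaffected.

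**What to change.** Add to the CRF, at both follow-ups, items for infection or antibiotics prescribed, malodorous discharge, worsening abdominal pain, other (specify) and serious adverse event (yes/no). Reconcile the fever wording between section 9.2 (≥ 38.0) and the CRF (> 38.0). State in any safety report that follow-up to about 4 weeks cannot rule out intra-uterine adhesions, so that a count of zero is not read as absence.

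The cost is a one-page form revision and slightly longer calls that are already planned. Because the form is an appendix to the protocol, the change would go to the ethics committee as an amendment under section 12.2. No extra visit, procedure or staff is needed, and care does not change.

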## 9.3 Assessment and Documentation of Adverse Events

Should there be concern that a patient is developing or has sustained an adverse event, they will be assessed clinically by ABS and/or AL. All possible adverse events will be documented in the study log.

#### 9.4 Serious Adverse Event (SAE) Reporting

#### 9.4.1 SAEs

For this study, a 'serious adverse event' is defined as any adverse event that occurs in the course of clinical research, and that: results in death; is life-threatening; requires hospitalisation or prolonged existing hospitalisation; or results in persistent or significant disability or incapacity.

# 9.4.2 Suspected Unexpected Serious Adverse Reaction (SUSAR)

For this study, a 'suspected unexpected serious adverse reaction' is defined as adverse events that are suspected to be related to an investigational procedure, and that are both unexpected and serious.

# 10 STATISTICAL METHODS

Regarding participants' answers to questions in the EHP-30 questionnaire: RedCap automatically exports data to statistical software SPSS, which will be used to perform the statistical analysis. Participants' BCL6 levels will be uploaded into the relevant section of the SPSS document used for this research, as will participants' endometriosis severity (based on the r-ASRM classification system).

Participants' BCL6 results will be continuous data, with their BCL6 HSCORE ranging from 0 to 4. Participants' endometriosis severity will be ordinal data, in that all participants will be categorised into one of five distinct groups: no endometriosis; stage I (minimal) endometriosis; stage II (mild) endometriosis; stage III (moderate) endometriosis; or stage IV (severe) endometriosis. It is expected that participants' BCL6 results by endometriosis severity will be presented in a boxplot.

Receiver-operator characteristic analysis will be performed to assess the usefulness of the biomarker and to find the optimal cut-off score for BLC6 that differentiates best between cases and controls.

Students t test will be used to compare mean BLC6 levels between cases and controls.

Regarding participants' EHP-30 questionnaire results: logistic regression analysis and a multi-variable model will enable us to ascertain whether including particular aspects of the long-form EHP-30 improves the predictive value of BCL6 in finding endometriosis at laparoscopy. If any such relationships are found, it is expected that these results could be presented as a nomogram, or classification tree analysis.

The statistical comparisons will be performed using statistical software SPSS (IBM), with P values < 0.05 considered significant.

#### 10.1 Sample Size Estimation

Our estimated sample size of 184 patients is based on the following assumptions:

- (1) For approximately one-third of our patient population, endometriosis is not suspected preoperatively (i.e. laparoscopy performed for another indication, such as laparoscopic myomectomy)
- (2) Approximately 10% of these patients will be found to have endometriosis at laparoscopy
- (3) For approximately two thirds of our patient population, endometriosis is expected to be found at laparoscopy
- (4) Approximately 50% of these patients will be found to have endometriosis at laparoscopy

This gives an overall prevalence of endometriosis of approximately 37% amongst our patient population. Assuming the sensitivity and specificity of BCL6 testing for endometriosis are at least 85% (from Evans-Hoeker et al), the sample size of 184 will provide precision of +/- 10% for 95% confidence intervals. We will need to recruit 68 patients who are found to have endometriosis at laparoscopy, and 116 who are not.

The sample size of 184 patients will provide 80% power to detect a difference of 0.374 in average BLC6 levels between controls (women without endometriosis at laparoscopy) and cases (women with endometriosis at laparoscopy) using a two-sided 5% significance level.

## 10.2 Population to be analysed

Women aged 18-50yo with regular menstrual cycles (21 - 35 days' duration, inclusive), who are planned to have laparoscopic surgery with the research team for any indication.

#### 10.3 Statistical Analysis Plan

Regarding participants' answers to questions in the EHP-30 questionnaire: RedCap automatically exports data to statistical software SPSS, which will be used to perform the statistical analysis. Participants' BCL6 levels will be uploaded into the relevant section of the SPSS document used for this research, as will participants' endometriosis severity (based on the r-ASRM classification system).

Participants' BCL6 results will be continuous data, with their BCL6 HSCORE ranging from 0 to 4. Participants' endometriosis severity will be ordinal data, in that all participants will be categorised into one of five distinct groups: no endometriosis; stage I (minimal) endometriosis; stage II (mild) endometriosis; stage III (moderate) endometriosis; or stage IV (severe) endometriosis. It is expected that participants' BCL6 results by endometriosis severity will be presented in a boxplot.

Receiver-operator characteristic analysis will be performed to assess the usefulness of the biomarker and to find the optimal cut-off score for BLC6 that differentiates best between cases and controls.

Students t test will be used to compare mean BLC6 levels between cases and controls.

Regarding participants' EHP-30 questionnaire results: logistic regression analysis and a multi-variable model will enable us to ascertain whether including particular aspects of the long-form EHP-30 improves the predictive value of BCL6 in finding endometriosis at laparoscopy. If any such relationships are found, it is expected that these results could be presented as a nomogram, or classification tree analysis.

The statistical comparisons will be performed using statistical software SPSS (IBM), with P values < 0.05 considered significant.

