(women without endometriosis). A cut-off of 1.4 provides a positive likelihood ratio of 15.4, and a negative likelihood ratio of 0.04 for endometriosis.

Hence, we are proposing to undertake a prospective study, in which patients who are already undergoing laparoscopic surgery (for any indication) have concurrent endometrial biopsy collected, using dilatation and curettage method. The endometrial biopsy sample will be sent for laboratory analysis, to determine the participant's BCL6 level. The patient's endometriosis (or lack thereof) will be surgically staged according to the revised American Society of Reproductive Medicine (r-ASRM) classification system, which is the standard scoring system for endometriosis (please see Appendix 13.1). Statistical analysis will allow conclusions to be made, regarding to what extent BCL6 on endometrial biopsy are predictive of the presence/absence and stage of endometriosis. If so, this will further develop the possible use of BCL6 as a relatively non-invasive biomarker to improve patient counselling and management, potentially negating the need to stage their endometriosis laparoscopically.

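### The BCL6 cut-off is chosen on the same women whose accuracy is then estimated, the sample size presumes a fixed cut-off, and no stated analysis uses the published 1.4

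*Protocol*

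**What the plan says.** The analysis text in sections 10 and 10.3 is the same, and the synopsis agrees with it. ROC analysis is to judge the marker's usefulness and to "find the optimal cut-off score for BLC6 that differentiates best between cases and controls". The criterion for optimal is not defined. No threshold is named in advance, and there is no hold-out sample, cross-validation, bootstrap correction or later validation cohort.

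Section 10.1 rests the sample size on accuracy: "Assuming the sensitivity and specificity of BCL6 testing for endometriosis are at least 85" per cent, a figure taken from the cited case-control study, and then "the sample size of 184 will provide precision of +/- 10% for 95% confidence intervals". It adds the split: "We will need to recruit 68 patients who are found to have endometriosis at laparoscopy, and 116 who are not".

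Section 2.3 gives that study's threshold and performance: "A cut-off of 1.4 provides a positive likelihood ratio of 15.4, and a negative likelihood ratio of 0.04 for endometriosis". The value 1.4 does not recur in the objectives, the outcome measures or the analysis text.

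**The concern.** A cut-off that maximises separation in one sample partly fits the noise in that sample. Sensitivity and specificity computed at it in the same women are therefore too high on average, and more so for a weaker marker. An ordinary binomial interval at that cut-off treats it as given and ignores the search.

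The sample-size argument in section 10.1 also treats the threshold as given, so the precision it promises belongs to a different analysis from the one in section 10.3.

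At stake is the figure readers will carry away. Section 2.3 looks ahead to BCL6 possibly replacing laparoscopic staging. It also recalls an earlier endometrial-biopsy marker whose promising first results could not be replicated by several later groups. Another in-sample optimum would be weaker evidence on this point than an estimate at a threshold named beforehand.

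**Working it through.** **Inputs from the protocol.** N = 184, 68 cases, 116 controls, assumed sensitivity and specificity 0.85, target ±10 points, difference 0.374 with 80% power at two-sided 5% (all section 10.1); LR+ 15.4 and LR− 0.04 at 1.4 (section 2.3).

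**Step 1: the plan's own figure.** For a fixed threshold the half-width is 1.96 × √(p(1−p)/n).
- Cases: 1.96 × √(0.85 × 0.15/68) = 8.5 points.
- Controls: 1.96 × √(0.85 × 0.15/116) = 6.5 points.

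The stated ±10% is met as an upper bound. The split follows from 184 × 0.37 = 68.1. The formula has no term for choosing the threshold.

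**Step 2: what the cited likelihood ratios imply.** With Se/(1−Sp) = 15.4 and (1−Se)/Sp = 0.04, substitution gives 15.36 × Sp = 14.4. So Sp = 93.75% and Se = 15.4 × 0.0625 = 96.25%. The planning value of 85% is well below this.

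**Step 3: the effect for which the t-test is powered.** The protocol gives no SD. Back-solving, SD = 0.374 / [(1.96 + 0.842) × √(1/68 + 1/116)] = 0.374/0.428 = 0.87, a standardised difference of about 0.43.

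**Step 4: optimism at a chosen cut-off.** Simulation, 4,000 studies per row, 68 cases from N(d,1) and 116 controls from N(0,1). The cut-off maximises sensitivity + specificity. Apparent accuracy at that cut-off is compared with true accuracy at the same cut-off. The normal model, equal variances and the Youden criterion are assumptions.

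| Best attainable Se/Sp | AUC | Apparent Se/Sp | True Se/Sp | Youden, apparent vs true | Excess (points) |
|---|---|---|---|---|---|
| 85%/85% | 0.93 | 87.2/86.4 | 84.2/84.6 | 0.735 vs 0.688 | 4.7 |
| 75%/75% | 0.83 | 77.5/76.8 | 74.0/74.6 | 0.543 vs 0.486 | 5.7 |
| 65%/65% | 0.71 | 68.3/67.2 | 63.8/64.7 | 0.355 vs 0.285 | 7.0 |
| d = 0.43 (step 3) | 0.62 | 62.3/61.0 | 57.3/58.1 | 0.233 vs 0.154 | 7.9 |
| Useless marker | 0.50 | 55.2/53.8 | 49.5/50.5 | 0.090 vs 0.000 | 9.0 |

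Repeat runs put the 85%/85% excess at 4.4 to 4.7 points. For stronger markers the excess in Youden's index is 3.9 points at 90%/90% and 2.9 at 95%/95%.

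**Step 5: precision and coverage.** In the 85%/85% case the sampling SD of sensitivity and specificity is 5.4 and 5.2 points with a chosen cut-off, against 4.3 and 3.3 with a fixed one. Both nominal 95% Wilson intervals together cover the true accuracy at the chosen cut-off about 88% of the time at 85%/85%, and about 82% at d = 0.43. A fixed cut-off gives about 90% (0.95 × 0.95).

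**Step 6: a cut-off fixed in advance.** With the threshold set beforehand, the 85%/85% simulation returns 85.1%/85.1%, and the half-widths of step 1 apply. At about the accuracy of step 2, 65/68 gives an exact 95% interval of 87.6% to 99.1%, and 109/116 gives 88.0% to 97.5%. No extra women are needed.

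**The case against.** Six points can be made for the plan.

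- **Accuracy at the chosen cut-off is not promised outright.** Nowhere does the protocol say that sensitivity and specificity will be reported there. That is inferred from 10.1, which sizes for them, and 10.3, which names no other threshold. The inference is reasonable, but it is one.
- **The main comparison is untouched.** The primary objective concerns BCL6 expression in women with and without endometriosis, and the t-test serves it. The AUC can serve the aim of judging usefulness. Neither depends on a cut-off. A reader might infer that the study validates nothing; the documents support only that no cut-off is validated.
- **The data would still allow a test of 1.4.** HSCORE is kept continuous, so accuracy at 1.4 can be computed. A reader might conclude that the study can neither confirm nor refute the published threshold. That goes too far: the protocol does not commit to the test, but nothing prevents it.
- **The bias is modest at the planning values.** It is 2 to 3 points per measure, inside the ±10 target, and smaller if accuracy is nearer the published level. Section 10.1 assumes at least 85%.
- **Validating 1.4 is not a stated aim**, and it may not transfer. That depends on whether the assay and HSCORE scale in section 8 match the cited study, which the documents cannot settle.
- **Details could sit in a separate SAP.** Optimism correction, interval method and cut-off criterion often do. But 10.3 is itself titled as the statistical analysis plan and positively selects a data-derived cut-off.

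The first five limit the wording and the severity. The last does not remove the point, because the choice is made in the text at hand.

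**Conclusion.** The point holds in a limited form. The protocol derives its cut-off from the women on whom accuracy would be estimated, while its precision claim presumes a fixed threshold, and no stated analysis uses the published 1.4.

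Accuracy reported at the ROC-chosen cut-off would be optimistic by about 3 points for sensitivity and 2 for specificity at 85%/85%. In Youden's index that is 4 to 5 points, against about 3 points at 95%/95% and 6 to 8 for weaker markers; a useless marker would show 0.09. Ordinary intervals ignore the search, though at the planning values the loss of joint coverage is small (88% against 90%).

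These sizes rest on the equal-variance normal model and the Youden criterion, neither of which the protocol states. The t-test and AUC are not affected. Severity: should be fixed.

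**What to change.** In section 10.3, with the synopsis and section 10 brought into line:

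- Name as the main accuracy results the AUC with its 95% interval, and sensitivity, specificity and likelihood ratios at the published HSCORE cut-off of 1.4, with exact or Wilson 95% intervals for sensitivity and specificity. State that this assumes the assay and HSCORE scale in section 8 match those of the cited study.
- Keep the ROC-derived cut-off as exploratory. State its criterion, for example Youden's index. Report its sensitivity and specificity with a bootstrap optimism correction that repeats the cut-off search in every resample.
- Say in section 10.1 that the ±10% precision refers to the pre-specified cut-off.

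Make the change before BCL6 results are linked to laparoscopic findings; a threshold named after the curve has been seen is not pre-specified. The cost is a few sentences and a short bootstrap run, with no extra participants or data. The downside is slightly less favourable accuracy figures for the derived cut-off.

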#### **3 STUDY OBJECTIVES**

Our null hypothesis is that there is no correlation between BCL6 levels on luteal phase endometrial biopsy between control (no-endometriosis) and women with endometriosis.

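### Student's t-test on a bounded score with 68 cases and 116 controls misstates the standard error if cases are more variable; the Welch form avoids this at almost no cost

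*Protocol*

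**What the plan says.** Section 10.3 (repeated in the opening of section 10 and in the synopsis) fixes the comparison of BCL6 between women with and without endometriosis: "Students t test will be used to compare mean BLC6 levels between cases and controls". It names no unequal-variance or rank alternative. It describes the measurement as continuous data, "with their BCL6 HSCORE ranging from 0 to 4"; section 8 calls the same score semi-quantitative.

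Section 10.1 sets the group sizes: "We will need to recruit 68 patients who are found to have endometriosis at laparoscopy, and 116 who are not". It also attaches a power statement to the comparison of means: "The sample size of 184 patients will provide 80% power to detect a difference of 0.374 in average BLC6 levels", "using a two-sided 5% significance level". No SD accompanies the 0.374.

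The same plan has other analyses. ROC analysis is assigned to judging how useful the biomarker is and to finding a cut-off. Logistic and multivariable modelling cover the added value of EHP-30. Section 10.1 also bases the sample size on the precision of sensitivity and specificity. Section 2.3 cites over-expression of BCL6 in women with endometriosis and a cut-off of 1.4 on this score.

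**The concern.** Student's t-test estimates one common variance. With unequal group sizes that estimate is weighted towards the larger group, here the controls. If the smaller group has the larger spread, the standard error of the mean difference is understated, p-values are too small and confidence intervals too narrow.

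The protocol's own background makes that direction plausible. A score with a floor at 0, a cut-off of 1.4 and over-expression in cases suggests controls bunched towards the low end and cases spread further up the scale. At stake is the stated uncertainty of the case-control difference in BCL6, which is what the primary objective and the null hypothesis in section 3 are about ("Our null hypothesis is that there is no correlation between BCL6 levels on luteal phase endometrial biopsy" in cases and controls).

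**Working it through.** **Inputs.** From section 10.1: n₁ = 68 cases, n₀ = 116 controls, two-sided 5%, 80% power, difference 0.374. From section 10.3: Student's t-test. Assumed, because the protocol gives no spreads: k = case SD / control SD.

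**1. The plan's own power figure.** It cannot be reproduced directly because the SD is missing, so it is solved backwards. By the normal approximation the standardised difference for 80% power is (1.960 + 0.842) × √(1/68 + 1/116) = 2.802 × √0.02333 = 0.428. The exact noncentral t gives 0.430. The implied common SD is 0.374 / 0.430 = 0.87. This is a back-calculation under a common SD and a 68/116 split; a 92/92 split would imply 0.90. Power for 0.374 depends on the SD: 90% at 0.75, 80% at 0.87, 68% at 1.00, 50% at 1.25.

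**2. Pooled against true standard error**, in units of the control SD.
- True variance of the mean difference: V = k²/68 + 1/116.
- Variance the pooled test uses, on average: P = [(67k² + 115)/182] × (1/68 + 1/116).
- Ratio of standard errors: R = √(P/V).
- Approximate error rate of the nominal 5% test when the means are equal: 2 × [1 − Φ(1.96 R)].

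| k | V | P | R | Error rate, formula | Error rate, simulation (1,000,000 draws, normal data) |
|---|---|---|---|---|---|
| 0.5 | 0.01230 | 0.01689 | 1.17 | 2.2% | 2.2% |
| 1 | 0.02333 | 0.02333 | 1.00 | 5.0% | 5.0% |
| 1.5 | 0.04171 | 0.03406 | 0.90 | 7.65% | 7.7% |
| 2 | 0.06744 | 0.04909 | 0.85 | 9.4% | 9.4% |

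At k = 1.5 and k = 2 the pooled standard error is therefore about 10% and 15% too small. A nominal 95% interval for the mean difference covers about 100 − 7.65 = 92.4% and 100 − 9.4 = 90.6%, whatever the true difference is.

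**3. The Welch test in the same settings.** Its simulated error rate was 5.0% at every SD ratio tried, from 1:3 to 3:1.

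**4. What Welch costs if the spreads are equal.** At the difference for which Student's test has 80% power, simulation gave 80.0% for Student and 79.9% for Welch. Allowing for simulation differences, the loss is 0.1 to 0.2 percentage points.

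**5. Mann-Whitney as an alternative.** With equal centres and normal data at 68/116, its simulated error rate was roughly 6.5% at k = 1.5 and 8% at k = 2. It does not restore 5% under unequal spread.

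**6. Where 0.374 stands as discrimination.** Under equal-variance normality, AUC = Φ(0.430/√2) = 0.62. Sensitivity = specificity = 85% corresponds to 2 × 1.036 = 2.07 SD and AUC 0.93. At 68/116 the approximate 95% CIs (Hanley-McNeil) are 0.53 to 0.71 around 0.62 and 0.88 to 0.97 around 0.93, so an AUC interval separates these two situations clearly.

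**The case against.** The strongest reply is that the error-rate argument needs equal means with unequal spreads, whereas over-expression in cases implies unequal means, where rejecting is correct. If BCL6 is unrelated to endometriosis, both groups share one distribution and Student's test holds its level; simulation gave 4.9% with normal data and 4.9% with data floored on the 0–4 scale. This stands for the strict null. It does not rescue the interval: when the means differ and cases are more variable, the pooled standard error is still too small. It is also fair that pooling is inferred from the name of the test, and that the direction could be the opposite, making the test conservative.

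A reader might also infer more than the protocol supports:
- *That the t-test is the only hypothesis test.* It is not: logistic and multivariable modelling are planned under the same P < 0.05 rule.
- *That the t-test is meant to establish predictive value.* Section 10.3 gives that task to ROC analysis, and the t-test does fit the primary objective.
- *That AUC 0.62 contradicts the 85%/85% assumption.* The 0.374 is a smallest detectable difference for a sample size also justified by precision. Being able to detect less than the expected effect is no defect. The precision claim reproduces: 1.96 × √(0.85 × 0.15/68) = 8.5% and 1.96 × √(0.85 × 0.15/116) = 6.5%, both inside ±10%.
- *That a rank test would cure the problem.* Step 5 of the working shows that it would not.

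**Conclusion.** The point holds in a limited form. The protocol names a test that, as usually run, relies on equal variances, in a setting where group sizes are unequal and the smaller group may plausibly be the more variable. The effect is moderate and conditional: about 7.6% or 9.4% instead of 5% if the case SD is 1.5 or 2 times the control SD, about 2.2% if it is half, and no distortion if the distributions are the same. These figures rest on assumed SD ratios and normal data. The sample size of 184 is not challenged.

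The missing SD behind 0.374 is a minor matter of completeness. It means the 80% cannot be verified from the protocol; it does not show that the figure is wrong.

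**What to change.** - In section 10.3, the matching text at the opening of section 10 and the synopsis, replace Student's t-test by the unequal-variance (Welch) t-test, and report the mean difference in BCL6 with its Welch 95% CI.
- Report the AUC from the planned ROC analysis with a 95% CI, and say that the statement on usefulness rests on the CIs of AUC, sensitivity and specificity.
- Minor: in section 10.1, give the SD actually used for the 0.374. The implied value of about 0.87 is a check for the sponsor to compare against, not a figure to adopt.

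The cost is wording only. Recruitment, data collection and sample size do not change, and the loss of power with equal spreads is at most about 0.2 percentage points.
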